8.1.2. QTc Stopping Criteria

- The *same* QT correction formula *must* be used for *each individual participant* to determine eligibility for and discontinuation from the study. This formula may not be changed or substituted once the participant has been enrolled.
 - For example, if a participant is eligible for the protocol based on QTcB, then QTcB must be used for discontinuation of this individual participant as well.
 - Once the QT correction formula has been chosen for a participant’s eligibility, the *same formula* must continue to be used for that participant *for all QTc data being collected for data analysis*. Safety ECGs and other non-protocol specified ECGs are an exception.
- The QTc should be based on single or averaged QTc values of triplicate electrocardiograms obtained over a brief (e.g., 5-10 minute) recording period.

See the SoA for data to be collected at the time of treatment discontinuation and follow-up and for any further evaluations that need to be completed.

In addition a healthy volunteer that meets either bulleted criterion below will be withdrawn from the study:

- QTc >500 msec,
- Change from baseline: QTcF >60 msec

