
Adverse effects due to reduction of 3 hydroxykynurenone (3HK) levels below the physiological range.
	
KMO deficient mice have undetectable levels of 3HK and elevation of metabolites, such as kynurenone (KYN), kynurenic acid (KYNA) and anthranilic acid (AA), but are viable and healthy. Robust increases in KYN, KYNA, AA and decreases in xanthurenic acid (XA) and quinolinic (QA) were measured in both rats and dogs in the 7-day dose range finding studies. Additionally a robust decrease in 3HK was observed in the dog study. 3HK levels could not be determined in the rat study. However the mid dose used in this rat study had previously been shown to reduce 3HK levels on the first day of dosing in a pharmacology study. Any adverse effects of changes in any of the TRP metabolites, including 3HK, would have been noted in these studies.
 
No information on the dynamics of the pathway after KMO inhibition in man is available and specific data on the rate of recovery of tryptophan metabolites, including 3HK, after
	
General safety monitoring will be conducted throughout the study, dose escalation criteria and stopping criteria (summarized in Appendix 3, Dose Escalation Committee), and a sentinel dosing approach (Section 5.1.1 and Section 5.1.2) have been outlined in the protocol.
 
Based on preliminary PK data from the initial two dose levels in Part A (SAD) a conservative safety observation period of 168 hours after single bolus infusion and after cessation of dosing in the 7-day continuous infusion study in a domiciled setting was chosen; 3HK data from humans is not available yet. The safety observation period will be reassessed based on emerging safety, PK and PD data during the trial.
 
Additional 3HK samples may be collected based on emerging data.

Potential Risk of Clinical Significance	Summary of Data/Rationale for Risk	Mitigation Strategy
	
treatment with GSK3335065 is not available from preclinical studies. Published studies with related KMO inhibitors have shown that recovery of metabolites typically occurs within 24-48hr after a bolus dose in rats (Mole et al 2016; Liddle et al, 2017 although 3HK itself was not measured in these studies.
	

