8.1.4. Additional Stopping Criteria

This section provides vital sign (blood pressure, heart rate), respiratory, oral temperature, and neuropsychiatric criteria for discontinuation of GSK 3335065 infusion. If criteria specified for action here are met, actions must be followed. Study investigators may also decide to discontinue dosing based on their clinical judgement for observations that are not specifically meet these thresholds, if they feel this is appropriate for best ensuring the safety of study subjects.

Blood Pressure:

- Resting semi-recumbent systolic blood pressure (SBP) of ≤ 80 mmHg that is confirmed (median of 3 measurements, and at least 20% decrease from baseline) and sustained for ≥ 20 min with or without symptoms of hypotension. Sustained is defined as persistent (threshold is met or exceeded on all rechecks over a 20 min period; minimum of 3 consecutive measurements over a 20 min interval)
- Resting semi-recumbent SBP ≥ 80 mmHg but ≤ 100 mHg that is confirmed (median of 3 measurements) and sustained if associated with symptoms of hypotension (e.g. fainting, lightheadedness, dizziness, anxiety)
- Hypotension requiring intervention such as Trendelenburg position w/wo fluid resuscitation
- Resting semi-recumbent SBP ≥ 180 mmHg that is confirmed (median of 3 measurements, and at least 20% increase from baseline with or without symptoms of hypertension (e.g. headaches, lightheadedness, anxiety)

Heart Rate:

- Tachycardia (resting semi-recumbent heart rate >100 bpm) of any duration associated with symptoms that the study investigator considers potentially associated with cardiac ischemia and/or hemodynamic compromise. Concerning symptoms might include chest pain, shortness of breath or lightheadedness.
- Resting semi-recumbent heart rate of ≥ 130 bpm that is confirmed (median of 3 measurements) and sustained. Sustained is defined as persistent (threshold is met or exceeded on all rechecks over a 20 min period; minimum of 3 consecutive measurements over a 10 min interval).
- Increase in resting semin-recumbent heart rate ≥ 60 bpm from the predose baseline (median of 3 measurements and sustained).

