If a vital sign threshold is exceeded which may result in discontinuation as defined above, the vital sign should immediately be repeated twice (i.e 3 measurements within approximately 5 minutes) and the median value will be used at that time point. If the median value exceeds the threshold, it will be considered confirmed that the value exceeded the potential discontinuation threshold and the subject must be discontinued.

Cardiac Troponin/ B-type Natriuretic Peptide (BNP):

If the local cardiac troponin (cTn) is >ULN or B-type Natriuretic Peptide (BNP) is >2x ULN for the assay, that subject will undergo repeat cTn or BNP testing and urgent evaluation if symptoms suggestive of cardiac ischemia or heart failure are present, and a transthoracic echocardiogram will be performed.

Asymptomatic volunteers: If the repeat value is within the normal range, the subject may continue in the study with close follow-up of symptoms. If the repeat value for cTn is >ULN or BNP is >2x ULN the subject must be discontinued from the study.

Symptomatic volunteers: Cardiology consultation will be obtained immediately for any subject with new signs or symptoms suggestive of cardiac ischemia or heart failure and the subject must be discontinued from the study. Concerning symptoms may include:

- chest pain,
- increased shortness of breath
- rapid or irregular heartbeat
- diaphoresis
- anxiety
- fatigue, tiredness
- confusion

Tympanic Temperature:

- Confirmed (median of 3 measurements) $\geq 38.5^{\circ}\text{C}$ at any time point between bolus/infusion initiation and 1 hour after completion of the dosing.

Respiratory Issues:

- In case the subject complains of dyspnea or shortness of breath, or if there is objective evidence of bronchospasm or other respiratory difficulty, the subject will be immediately evaluated and if confirmed the subject must be discontinued from the study.

Neuropsychiatric Issues:

Suicidal Ideation and Behaviour:

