If Columbia Suicide Severity Rating Scale (C-SSRS) and/or PSRAE assessments indicate a clinically relevant increase in suicidal ideation or behavior or a subject shows new signs or symptoms during the infusion period suggestive of an increase in suicidal ideation and behavior psychiatric consultation will be obtained and the Sponsor's Medical Monitor should be contacted. Discontinuation is mandated in case the patient scores "yes" on item four or item five of the Suicidal Ideation Section of the Columbia Suicide Severity Rating Scale (C-SSRS) or "yes" on any item of the Suicidal Behaviour Section. In addition, study investigators may also decide to discontinue dosing based on their clinical judgment for observations that do not specifically meet these thresholds, if they feel this is appropriate for best ensuring the safety of study subjects.

Cognitive Safety:

- If cognitive test results (i.e. fittapping test [FTT], 6-item cognitive impairment test [6-CIT], Neuropsychiatric Inventory [NPI]) indicate a clinically significant

effect of GSK3335065 on cognitive safety or the subject shows new signs or symptoms during the infusion period suggestive of an effect on cognitive safety, psychiatric consultation should be obtained and the Sponsor's Medical Monitor should be contacted. If the increased risk can be confirmed the subject must be discontinued from the study.

In case there is objective evidence that a subject is in psychological distress, the subject will be immediately evaluated and the subject must be discontinued from the study if the investigators based on their clinical evaluation feel this is appropriate for best ensuring the safety of study subjects. Concerning symptoms might include:

- Nervousness,
- Anxiety, irritability
- Sudden worsening of mood
- Sudden outbursts of anger ("anger attacks")
- Sudden panic or anxiety attacks
- Agitation
- Feeling unreal or detached
- Confusion or trouble concentrating
- Forgetfulness or problems with memory
- Mood swings
- Trouble sleeping, insomnia
- Fatigue, tiredness

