8.2. Withdrawal from the Study

- A participant may withdraw from the study at any time at his/her own request, or may be withdrawn at any time at the discretion of the investigator for safety, behavioral, compliance or administrative reasons.
- If the participant withdraws consent for disclosure of future information, the sponsor may retain and continue to use any data collected before such a withdrawal of consent.
- If a participant withdraws from the study, he/she may request destruction of any samples taken and not tested, and the investigator must document this in the site study records.
- Refer to the Schedule of Activities ((SOA) Section 2) for data to be collected at the time of study discontinuation and follow-up and for any further evaluations that need to be completed.

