12.7. Appendix 7: Liver Safety: Required Actions and Follow-up Assessments

Phase I Liver chemistry stopping criteria have been designed to assure subject safety and to evaluate liver event etiology (in alignment with the FDA premarketing clinical liver safety guidance).

<http://www.fda.gov/downloads/Drugs/GuidanceComplianceRegulatoryInformation/Guidances/UCM174090.pdf>.

Phase I liver chemistry stopping criteria and required follow up assessments

Liver Chemistry Stopping Criteria – Liver Stopping Event	
ALT-absolute ALT \geq 3xULN If ALT \geq 3xULN AND bilirubin ^{1,2} \geq 2xULN (>35% direct bilirubin) or INR $>$ 1.5, Report as an SAE. See additional Actions and Follow Up Assessments listed below	
Required Actions and Follow up Assessments following Liver Stopping Event	
Actions	Follow Up Assessments

 • Immediately discontinue study treatment • Report the event to GSK within 24 hours • Complete the liver event CRF, and complete an SAE data collection tool if the event also meets the criteria for an SAE² • Perform liver event follow up assessments • Monitor the subject until liver chemistries resolve, stabilise, or return to within baseline (see MONITORING below) 
MONITORING:
 
If ALT\geq3xULN AND bilirubin \geq 2xULN or INR $>$1.5
 
 • Repeat liver chemistries (include ALT, AST, alkaline phosphatase, bilirubin) and perform liver event follow up assessments within 24 hrs • Monitor subjects twice weekly until liver chemistries resolve, stabilise or return to within baseline • A specialist or hepatology consultation is 	
 • Viral hepatitis serology³ • Blood sample for pharmacokinetic (PK) analysis, obtained according to PK sampling schedule • Serum creatine phosphokinase (CPK) and lactate dehydrogenase (LDH). • Fractionate bilirubin, if total bilirubin\geq2xULN • Obtain complete blood count with differential to assess eosinophilia • Record the appearance or worsening of clinical symptoms of liver injury, or hypersensitivity, on the AE report form • Record use of concomitant medications on the concomitant medications report form including acetaminophen, herbal remedies, other over the counter medications. • Record alcohol use on the liver event alcohol intake case report form 
If ALT\geq3xULN AND bilirubin \geq 2xULN or

Liver Chemistry Stopping Criteria – Liver Stopping Event	

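### Several safety rules filed under stopping treatment take the subject out of the study, and the schedule they point to has no early-discontinuation column

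*Protocol*

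**What the plan says.** Protocol 8.1 deals with stopping study treatment; withdrawal from the study is a separate section, 8.2. Section 8.1.4 introduces its contents as vital-sign, respiratory, temperature and "neuropsychiatric criteria for discontinuation of GSK 3335065 infusion".

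The written consequences go further. For QTc, 8.1.2 says "In addition a healthy volunteer that meets either bulleted criterion below will be withdrawn from the study". For asymptomatic subjects with raised cardiac markers, 8.1.4 says "If the repeat value for cTn is >ULN or BNP is >2x ULN the subject must be discontinued from the study". For cognition it says "If the increased risk can be confirmed the subject must be discontinued from the study". The cardiac-symptom and confirmed respiratory rules in 8.1.4 have the same consequence.

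For what to collect afterwards, 8.1.2 says "See the SoA for data to be collected at the time of treatment discontinuation and follow-up", and 8.2 again refers to the SoA "for data to be collected at the time of study discontinuation and follow-up".

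With subjects resident in the unit, Section 3.3.1 commits to "a conservative safety observation period of 168 hours after single bolus infusion and after cessation of dosing in the 7-day continuous infusion study". Section 5.4.1 explains that PK sampling was lengthened because the half-life proved much longer than predicted.

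The liver rule in Appendix 7 is worded differently. Its action is "Immediately discontinue study treatment", followed by liver monitoring and a PK sample taken on the PK schedule.

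**The concern.** In Part A and Cohort 13 the whole dose has been given before any of these criteria can be met. Stopping treatment then has no content, and leaving the study removes no exposure. What it can remove is observation. If a site reads the rule literally, the scheduled ECG, vital-sign, PK and 3HK/KYN time course may end before 168 h in a subject who has just shown a QTc, cardiac-marker, respiratory or cognitive signal.

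Data up to the exit are kept and used (SAP 11.7.1), and the triggering value still reaches the dose review. The part at risk is the profile afterwards. AUC(0-inf), CL, V and half-life, all secondary PK endpoints, could be poorly estimated or absent for that subject, and so could the recovery of 3HK and KYN. With six active subjects per cohort, later time-point summaries would come from the subjects who had no signal. Readings taken only because of the event may count as unscheduled, and SAP 11.5.2 lists unscheduled visits but keeps them out of summary tables and figures. SAP 11.7.1 also rules out replacement of withdrawn subjects in Part A Cohorts 3-8, although Protocol 5.2 is more permissive.

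**Working it through.** **1. Consequence written for each criterion**

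- QTc (8.1.2): out of the study.
- Confirmed cTn/BNP, cardiac symptoms, confirmed respiratory event, confirmed cognitive risk (8.1.4): out of the study.
- Psychological distress (8.1.4): out of the study, at the investigator's judgement.
- Blood pressure, heart rate, temperature and C-SSRS (8.1.4): discontinuation, without saying from the study. These are not part of the point.
- Liver (Appendix 7): study treatment stopped.

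**2. What the SoA offers a stopped subject**

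SoA 2.1 has Screening, Day -1, Days 1-8 and a follow-up visit 7-14 days after discharge. SoA 2.2 has Screening, Day -1, Days 1-15, follow-up on Day 32 and an LFT visit on Day 62. Neither has an early-discontinuation column or a note on which assessments remain due. Whether cTnI/BNP are drawn at the bolus-cohort follow-up is unclear: their own row shows no mark there, but the safety-laboratory row does, and Table 15 lists both tests. They are therefore left out of the count below.

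**3. Scheduled times after a stop, Part A Cohorts 3-8**

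Post-dose times come from 9.5.1 (PK), 9.7 (PD) and the notes in SoA 2.1 (ECG: 0.5, 6, 12, 24, 72, 120, 168 h; vital signs: 0.5, 1, 6, 24, 48, 72, 96, 120, 144, 168 h). The stop times are assumptions; the documents give no frequency or timing for such events.

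| Assumed stop | PK (28) | PD (28) | ECG (7) | Vital signs (10) |
|---|---|---|---|---|
| 6 h | 19 | 19 | 5 | 7 |
| 24 h | 14 | 14 | 3 | 6 |
| 72 h | 8 | 8 | 2 | 4 |

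These are the times that could be lost on a literal reading.

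**4. Share of AUC(0-inf) beyond the last sample**

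Input: observed preliminary half-life of about 35 h (9.3). For one exponential phase the share beyond time t is 2^(-t/35). For a sum of positive exponentials whose slowest half-life is 35 h, every other phase decays faster, so this value is an upper bound.

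- 24 h: 2^(-24/35) = 0.622, at most 62%
- 72 h: 2^(-72/35) = 0.240, at most 24%
- 168 h: 2^(-168/35) = 0.036, at most 3.6%

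Sampling to 24 h covers 24/35 = 0.69 half-lives; sampling to 168 h covers 168/35 = 4.8.

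**5. Is the 62% bound likely to be reached?**

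AUC(0-24) for one phase is (dose/V) x (t1/2 / ln 2) x (1 - 2^(-24/t1/2)). Per unit of dose/V:

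- 35 h: 50.5 x 0.378 = 19.1
- 7.8 h, the predicted half-life in 5.4.1: 11.25 x 0.881 = 9.9

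With V unchanged, a single 35 h phase would give 19.1/9.9, about 1.9 times the predicted 24 h exposure. Section 5.4.1 reports that 24 h exposure was generally in line with prediction. A single 35 h phase would therefore need roughly twice the predicted V. A multi-phase decline with a smaller share beyond 24 h is more likely.

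**The case against.** The strongest reply is that nothing in the protocol says that exit cancels the remaining schedule. Section 8.2 sends the site to the SoA for evaluations still to be completed, SoA discharge follows completion of all assessments, and Table 5 keeps bolus subjects in-house to Day 8. A reader might infer that no scheduled assessment is required between the stop and the follow-up visit, or that the subject must be sent home. The documents do not support either as a flat statement. This part of the objection stands: the defect is an ambiguity set against 3.3.1.

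Safety follow-up is also substantial. The protocol provides for:

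- extended telemetry (SoA notes);
- repeat cTn/BNP, echocardiogram and cardiology consultation (8.1.4);
- follow-up of related events and of those causing discontinuation of treatment (9.2);
- repetition of clinically significant laboratory tests (9.4.6);
- measurements requested by the sponsor (Appendix 4);
- extra visits if warranted (Tables 4-8) and optional extra PK/PD samples (9.5.1, 9.7).

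This stands too, so an inference that stopped subjects go unmonitored would be wrong. None of these provisions, however, requires the scheduled PK/PD profile.

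For the infusion cohorts, a reader might take the SoA columns to mean that a subject stopped on Day 1 has nothing due until Day 32. That ignores 9.5.1 and 9.7, whose PK and PD times after treatment run from the end of the infusion, and 3.3.1, which counts 168 h from the end of dosing. What remains unclear there is that the study-day labels assume a completed infusion.

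Appendix 7 should not be over-read either. It shows a stop limited to treatment, with liver follow-up and a PK sample. It does not say that the subject stays in the study, and it does not ask for continued PD, ECG or vital-sign profiles.

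Finally, withdrawing a healthy volunteer with no prospect of benefit is a defensible cautious choice, no hypotheses are tested, and PK parameters are derived only where data permit. That limits the importance of the point. It does not explain why leaving the study is the chosen action once the bolus is already in.

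**Conclusion.** The point holds as a minor one. Five criteria placed under treatment discontinuation remove the subject from the study, and the SoA they rely on does not say what is then due. On a literal reading, a stop at 24 h in Part A Cohorts 3-8 could cost half of the PK and PD times, 3 of 7 ECGs and 6 of 10 vital-sign times.

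Up to 62% of AUC(0-inf) could lie beyond the last sample. This rests on positive exponential phases with a slowest half-life of 35 h, and the true share is probably lower. A reader might be tempted to use the predicted 7.8 h half-life for a lower limit, which gives 2^(-24/7.8) = 12%. Section 5.4.1 contradicts that half-life, and a single 7.8 h phase is not a lower bound for a multi-phase decline, so no lower limit is given.

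The SAP introduction and SAP 3.1 report that the study ended during Cohort 3 after ventricular tachycardia, handled as a SUSAR and so subject to SAE follow-up. The documents do not say whether any subject left under 8.1.2 or 8.1.4, so the effect on the data collected may be nil.

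**What to change.** Keep every threshold. Then:

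- In 8.1.2 and 8.1.4, state that these criteria stop study treatment where it is still running, and that the subject stays in the study for the remaining SoA safety, PK and PD assessments through follow-up, as medically feasible and unless consent is withdrawn.
- For an infusion stopped early, state that the existing post-infusion PK/PD times and the 168 h observation run from the actual end of dosing.
- Mark cTnI/BNP explicitly at follow-up for subjects stopped for a cardiac reason.

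With this study ended, the practical use is in any successor protocol. The study report could also say whether anyone left under these criteria.

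The cost is a few sentences and an SoA mark. The assessments are already planned for every subject, so planned blood volume does not rise, apart from cTnI/BNP at follow-up if the safety laboratories do not already include them. The downside is that a few stopped subjects complete visits and draws they might otherwise skip. After a 24 h stop in Part A Cohorts 3-8 that is up to 14 PK draws of 1 mL and 14 PD draws of 2 mL, or 14 + 28 = 42 mL. Some subjects under cardiology or psychiatric care will be unable to complete them, which is why the wording needs the medical-feasibility clause.

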8.1.3. Rechallenge

8.1.3.1. Study Treatment Restart or Rechallenge

Study treatment restart or rechallenge after liver chemistry stopping criteria are met by any participant in this study is not allowed.

8.1.4. Additional Stopping Criteria

This section provides vital sign (blood pressure, heart rate), respiratory, oral temperature, and neuropsychiatric criteria for discontinuation of GSK 3335065 infusion. If criteria specified for action here are met, actions must be followed. Study investigators may also decide to discontinue dosing based on their clinical judgement for observations that are not specifically meet these thresholds, if they feel this is appropriate for best ensuring the safety of study subjects.

Blood Pressure:

- Resting semi-recumbent systolic blood pressure (SBP) of ≤ 80 mmHg that is confirmed (median of 3 measurements, and at least 20% decrease from baseline) and sustained for ≥ 20 min with or without symptoms of hypotension. Sustained is defined as persistent (threshold is met or exceeded on all rechecks over a 20 min period; minimum of 3 consecutive measurements over a 20 min interval)
- Resting semi-recumbent SBP ≥ 80 mmHg but ≤ 100 mHg that is confirmed (median of 3 measurements) and sustained if associated with symptoms of hypotension (e.g. fainting, lightheadedness, dizziness, anxiety)
- Hypotension requiring intervention such as Trendelenburg position w/wo fluid resuscitation
- Resting semi-recumbent SBP ≥ 180 mmHg that is confirmed (median of 3 measurements, and at least 20% increase from baseline with or without symptoms of hypertension (e.g. headaches, lightheadedness, anxiety)

Heart Rate:

- Tachycardia (resting semi-recumbent heart rate >100 bpm) of any duration associated with symptoms that the study investigator considers potentially associated with cardiac ischemia and/or hemodynamic compromise. Concerning symptoms might include chest pain, shortness of breath or lightheadedness.
- Resting semi-recumbent heart rate of ≥ 130 bpm that is confirmed (median of 3 measurements) and sustained. Sustained is defined as persistent (threshold is met or exceeded on all rechecks over a 20 min period; minimum of 3 consecutive measurements over a 10 min interval).
- Increase in resting semin-recumbent heart rate ≥ 60 bpm from the predose baseline (median of 3 measurements and sustained).

If a vital sign threshold is exceeded which may result in discontinuation as defined above, the vital sign should immediately be repeated twice (i.e 3 measurements within approximately 5 minutes) and the median value will be used at that time point. If the median value exceeds the threshold, it will be considered confirmed that the value exceeded the potential discontinuation threshold and the subject must be discontinued.

Cardiac Troponin/ B-type Natriuretic Peptide (BNP):

If the local cardiac troponin (cTn) is >ULN or B-type Natriuretic Peptide (BNP) is >2x ULN for the assay, that subject will undergo repeat cTn or BNP testing and urgent evaluation if symptoms suggestive of cardiac ischemia or heart failure are present, and a transthoracic echocardiogram will be performed.

Asymptomatic volunteers: If the repeat value is within the normal range, the subject may continue in the study with close follow-up of symptoms. If the repeat value for cTn is >ULN or BNP is >2x ULN the subject must be discontinued from the study.

Symptomatic volunteers: Cardiology consultation will be obtained immediately for any subject with new signs or symptoms suggestive of cardiac ischemia or heart failure and the subject must be discontinued from the study. Concerning symptoms may include:

- chest pain,
- increased shortness of breath
- rapid or irregular heartbeat
- diaphoresis
- anxiety
- fatigue, tiredness
- confusion

Tympanic Temperature:

- Confirmed (median of 3 measurements) $\geq 38.5^{\circ}\text{C}$ at any time point between bolus/infusion initiation and 1 hour after completion of the dosing.

Respiratory Issues:

- In case the subject complains of dyspnea or shortness of breath, or if there is objective evidence of bronchospasm or other respiratory difficulty, the subject will be immediately evaluated and if confirmed the subject must be discontinued from the study.

Neuropsychiatric Issues:

Suicidal Ideation and Behaviour:

If Columbia Suicide Severity Rating Scale (C-SSRS) and/or PSRAE assessments indicate a clinically relevant increase in suicidal ideation or behavior or a subject shows new signs or symptoms during the infusion period suggestive of an increase in suicidal ideation and behavior psychiatric consultation will be obtained and the Sponsor's Medical Monitor should be contacted. Discontinuation is mandated in case the patient scores "yes" on item four or item five of the Suicidal Ideation Section of the Columbia Suicide Severity Rating Scale (C-SSRS) or "yes" on any item of the Suicidal Behaviour Section. In addition, study investigators may also decide to discontinue dosing based on their clinical judgment for observations that do not specifically meet these thresholds, if they feel this is appropriate for best ensuring the safety of study subjects.

Cognitive Safety:

- If cognitive test results (i.e. fittapping test [FTT], 6-item cognitive impairment test [6-CIT], Neuropsychiatric Inventory [NPI]) indicate a clinically significant

effect of GSK3335065 on cognitive safety or the subject shows new signs or symptoms during the infusion period suggestive of an effect on cognitive safety, psychiatric consultation should be obtained and the Sponsor's Medical Monitor should be contacted. If the increased risk can be confirmed the subject must be discontinued from the study.

In case there is objective evidence that a subject is in psychological distress, the subject will be immediately evaluated and the subject must be discontinued from the study if the investigators based on their clinical evaluation feel this is appropriate for best ensuring the safety of study subjects. Concerning symptoms might include:

- Nervousness,
- Anxiety, irritability
- Sudden worsening of mood
- Sudden outbursts of anger ("anger attacks")
- Sudden panic or anxiety attacks
- Agitation
- Feeling unreal or detached
- Confusion or trouble concentrating
- Forgetfulness or problems with memory
- Mood swings
- Trouble sleeping, insomnia
- Fatigue, tiredness

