3.3.1. Risk Assessment

Potential Risk of Clinical Significance	Summary of Data/Rationale for Risk	Mitigation Strategy
Investigational Product (IP) [GSK 3335065]		

Because cardiovascular (CV) changes were observed in rat safety assessments studies, there is a risk of cardiac-related adverse events being observed in man
	
In a rat preliminary dose range finding study via continuous infusion, increases in cardiac troponin I (cTnI) and N-terminal brain natriuretic peptide (NT-proANP) concentrations and degenerative and/or inflammatory changes in the heart were seen in rats given 300 mg/kg/day.
 
In a rat preliminary dose range finding study via oral gavage, myocardial necrosis and inflammatory cell infiltrate were seen in the hearts of rats given 400 mg/kg/day (with no changes in cardiac biomarkers).
	
The CV changes observed in rats were only noted at exposures 128-fold higher than the highest exposure predicted in this study and at concentrations 232-fold higher than those predicted in this study and were accompanied by changes in cardiac biomarkers that can be monitored (cTnI and brain natriuretic peptide [BNP]):
 
Subjects with cTn or BNP > ULN will be excluded (Exclusion criterion # 5)
 
Monitoring for cTn and BNP in all parts of the study (Section 2, Time and Events Table)
 
Stopping criteria based on cTn and BNP increases (Section 8.1.4)
 
Continuous ECG monitoring during the first 24hr after initiation of dosing, followed by 12-lead ECG assessments
 
The NOAEL for this effect is 75-fold the highest exposures and 177 times the concentration proposed in this study.

Potential Risk of Clinical Significance	Summary of Data/Rationale for Risk	Mitigation Strategy
Haemodynamic changes	
In a screening cardiovascular study in the rat, there were increases in blood pressure (maximum 12 mmHg), pulse pressure (maximum 5 mmHg), heart rate (maximum 63 bpm) and body temperature (0.7°C), and decreases in QA interval (maximum 5 msec).
	
No effect concentration in the rat (16.8µg/mL) was 4200-fold higher than the targeted concentration at starting dose (0.004µg/mL).
 
Regular Vital Sign (BP and HR) assessments during the study (Section 2 Time and Events Table)
 
Stopping criteria based on Vital Sign changes (Section 8.1.4)
 
Continuous ECG monitoring during initial 24hrs after initiation of dosing, followed by 12-lead ECG assessments.

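### The two numeric hypotension stopping rules leave a gap: a symptomatic, sustained SBP below 80 mmHg with a fall of less than 20% meets neither, although a milder reading in the same subject is a mandatory stop

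*Protocol*

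**What the plan says.** Section 8.1.4 (Additional Stopping Criteria) makes its actions mandatory once a criterion is met. Three blood-pressure bullets concern hypotension.

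- **Bullet 1.** The limit is an SBP of 80 mmHg or less. The reading must be one "that is confirmed (median of 3 measurements, and at least 20% decrease from baseline"). The 20% fall is thus part of what counts as confirmed. On duration and symptoms the bullet asks for a reading "sustained for ≥ 20 min with or without symptoms of hypotension", so symptoms make no difference.
- **Bullet 2.** "Resting semi-recumbent SBP ≥ 80 mmHg but ≤ 100 mHg that is confirmed (median of 3 measurements"), sustained, and accompanied by symptoms of hypotension. It has no condition on the fall from baseline.
- **Bullet 3.** Hypotension that needs an intervention, with no numeric limit.

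Two further provisions bear on the point. For observations outside the thresholds, "Study investigators may also decide to discontinue dosing based on their clinical judgement". A later paragraph on repeat measurement begins "If a vital sign threshold is exceeded which may result in discontinuation as defined above". It says that when the median of three readings is beyond the threshold, the value is confirmed and the subject must stop.

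Sections 6.1 and 6.2 set no lower limit on SBP at entry.

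**The concern.** A stopping rule for hypotension should not become less strict as pressure falls. Here it can. Below 80 mmHg, bullet 2 no longer applies, and bullet 1 applies only if the fall has reached 20%. In a subject with a low-normal baseline, a symptomatic reading in the 70s can lose the mandatory stop that a reading in the low 80s would have triggered.

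At stake is whether stopping a symptomatic healthy volunteer is required or left to discretion. This matters most in the seven-day infusion cohorts (9 to 12 and 14), where dosing remains to be stopped. After a single bolus there is no infusion to halt.

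**Working it through.** **Inputs.** All come from Section 8.1.4: bullet 1 has a limit of 80 mmHg and a fall of at least 20%; bullet 2 has limits of 80 and 100 mmHg and requires symptoms. The plan states no figure to reproduce. Let *B* be baseline SBP and *S* the confirmed, sustained reading in a symptomatic subject.

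**Rules as formulas.**
- Bullet 1 is met if *S* ≤ 80 and (*B* − *S*)/*B* ≥ 0.20, that is, *S* ≤ 0.8*B*.
- Bullet 2 is met if 80 ≤ *S* ≤ 100.
- Neither is met, for *S* ≤ 100, if 0.8*B* < *S* < 80.

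**When the gap exists.** The interval is non-empty only if 0.8*B* < 80, so *B* < 100 mmHg. The highest whole-number reading below 80 is 79. It is uncovered when *B* < 79/0.8 = 98.75 mmHg, so for whole-number baselines the gap starts at 98.

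**Worked example, baseline 95 (0.8 x 95 = 76).**

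| Symptomatic SBP | Fall | Bullet 1 | Bullet 2 | Mandatory stop under bullets 1–2 |
|---|---|---|---|---|
| 81 | 14/95 = 14.7% | no | yes | yes |
| 79 | 16/95 = 16.8% | no | no | **no** |
| 77 | 18/95 = 18.9% | no | no | **no** |
| 76 | 19/95 = 20.0% | yes | no | yes |

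At exactly 80 mmHg with symptoms bullet 2 applies, so the gap lies strictly below 80.

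**Width by baseline, whole-number readings.**

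| Baseline | 0.8 x baseline | Uncovered readings | Count |
|---|---|---|---|
| 99 or above | 79.2 or above | none | 0 |
| 98 | 78.4 | 79 | 1 |
| 95 | 76.0 | 77–79 | 3 |
| 92 | 73.6 | 74–79 | 6 |
| 90 | 72.0 | 73–79 | 7 |
| 85 | 68.0 | 69–79 | 11 |

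Summing the uncovered readings over baselines 85 to 98 gives 11+11+10+9+8+7+7+6+5+4+3+3+2+1 = 87 baseline/reading pairs. Baselines 80 to 84 add 15+15+14+13+12 = 69, for 156 in all. These totals depend on the range chosen and say nothing about likelihood.

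**Effect of the correction.** Without its floor, bullet 2 is met by any symptomatic *S* ≤ 100, so the uncovered pairs fall from 156 to 0. Bullet 2 never applies to asymptomatic subjects, so none of their outcomes changes.

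**Comparison with the SAP.** SAP Section 11.8.3 flags SBP below 85 mmHg as of potential clinical importance in absolute terms, with no percentage condition. Every reading in the gap is 79 mmHg or lower and would be flagged.

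**The case against.** The strongest reply is that Section 8.1.4 as a whole covers most of these cases.

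- **Bullet 3** sets a low bar. Repositioning the subject is enough, with or without fluids, and no reading, duration or baseline is needed. Few volunteers symptomatic in the 70s would be left without any intervention. This greatly reduces the practical gap, but stopping then depends on someone having intervened.
- **The confirmation paragraph** can be read as requiring a stop on the median alone, since it does not repeat the 20% fall. It refers back to thresholds as already defined, however, and bullet 1 puts the fall inside its own definition of confirmed. If the paragraph did override the bullets' qualifiers, it would also cancel bullet 2's symptom condition and force a stop in an asymptomatic subject at 95 mmHg. At best it is ambiguous.
- **Other rules** overlap in part. The symptomatic-tachycardia rule needs a heart rate above 100 bpm. The cardiac rule needs signs suggesting ischaemia or heart failure. Discretionary stopping is optional by its own wording.
- **The 20% condition looks deliberate**, since the hypertension bullet has it too. That supports keeping it for asymptomatic readings. It does not explain why bullet 2 has a floor.
- **Scope is narrow.** The gap needs a baseline below 100 mmHg, and the wider gaps need baselines near 90 or 85. The rat finding in Section 3.3.1 pointed the other way: "there were increases in blood pressure (maximum 12 mmHg"). SAP Sections 1 and 2.3 record that the study ended after sentinel dosing in Cohort 3 and that Parts B and C no longer apply, so no infusion subject met this rule.

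The points on scope stand and limit the weight of the concern. They do not make the rule correct as written.

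**Conclusion.** The concern holds. The two numeric bullets leave symptomatic SBP between 0.8 x baseline and 80 mmHg without a mandatory stop, while a milder symptomatic reading in the same subject has one. The gap is 3 mmHg readings wide at baseline 95, 7 at baseline 90, and absent at 99 or above.

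This assumes that the bullets are read as written, that the reading is confirmed and sustained, and that the confirmation paragraph does not override bullet 1's own definition of confirmed. The documents give neither a baseline SBP distribution nor a hypotension rate, so no estimate is made of how many subjects would be affected.

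It is a narrow defect in a general safety rule, with no effect on endpoints or analysis. It should be corrected because the criteria are mandatory and Section 3.3.1 lists vital-sign stopping criteria among its mitigations for haemodynamic risk. As the study has ended, the correction matters mainly for any reuse of the wording.

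**What to change.** In Section 8.1.4, delete the lower bound from the second blood-pressure bullet, so that it applies to any confirmed and sustained SBP of 100 mmHg or less with symptoms of hypotension. This change alone closes the gap.

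For consistency, limit the 20% condition in the first bullet to asymptomatic readings. This second edit is tidying.

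The cost is two phrases, with no new measurement, visit or sample.
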